2.3.2. Benefit Assessment

Ponsegromab has not been administered to patients with HF prior to this study. Based upon nonclinical data, it is hypothesized that dosing with ponsegromab will lessen participants' frequency and/or burden of symptoms associated with HF. Participants may benefit, clinically, from more intense monitoring and more frequent assessments compared to usual standard of care. Participants may benefit from contributing to research in heart failure and improving our understanding of the condition.

2.3.3. Overall Benefit/Risk Conclusion

Taking into account all available nonclinical and clinical data regarding the safety and tolerability of ponsegromab to date, and measures to monitor and minimize risk to study participants, the overall benefit/risk profile supports further clinical development of ponsegromab in participants with HF.

3. OBJECTIVES, ENDPOINTS, AND ESTIMANDS

3.1. Main Cohort (Cohort A), Cohort C and Cohort D

Objectives	Endpoints	Estimands
Primary:	Primary:	Primary:

 To compare the effect of ponsegromab 300 mg versus placebo, on HF disease-specific health status in participants with HF and serum GDF-15 concentrations CCI pg/mL (Main Cohort [Cohort A]) only. 	
 Change from baseline in KCCQ-23 CSS at Week 22. 	
 Estimand 1 (similar to "hypothetical") is the difference between ponsegromab and placebo in mean change from baseline in KCCQ-23 CSS at Week 22, in study participants with HF and serum GDF-15 concentrations CCI pg/mL, under the scenario of no discontinuation of study intervention and without the potential confounding effect of prohibited procedures or participants' non-compliance with dosing.
Secondary:	Secondary:	Secondary:

 To compare the effect of ponsegromab versus placebo on HF disease-specific overall health status in participants with HF and serum GDF-15 concentrations CCI pg/mL. 	
 Change from baseline in KCCQ-23 CSS, OSS, TSS, and physical limitation at Week 22. 	
 Estimand 2 (similar to "hypothetical") is the difference between ponsegromab and placebo in mean change from baseline in each of KCCQ-23 CSS, OSS, TSS and physical limitation score at Week 22, in participants with HF and serum GDF-15 concentrations CCI pg/mL, under the scenario of no discontinuation of study intervention and without the potential confounding effect of prohibited procedures or

Objectives	Endpoints	Estimands
		participants' non-compliance with dosing.

 To compare the effect of ponsegromab versus placebo on HF disease-specific health status in participants with HF and serum GDF-15 concentrations CCI pg/mL. 	
 Responses as defined by a ≥ 5-point increase from baseline in KCCQ-23 CSS, OSS, TSS, and physical limitation at Week 22. 	
 Estimand 3 (similar to "hypothetical") is the odds ratio between ponsegromab and placebo on the proportion of participants with ≥ 5-point increases from baseline in each of KCCQ-23 CSS, OSS, TSS, and physical limitation score at Week 22, in participants with HF and serum GDF-15 concentrations CCI pg/mL, under the scenario of no discontinuation of study intervention and without the potential confounding effect of prohibited procedures or participants' non-compliance with dosing.

 To compare the effect of ponsegromab versus placebo on the physical function of participants with HF and serum GDF-15 concentrations CCI pg/mL. 	
 Change from baseline in 6MWD at Week 22. 	
 Estimand 4 (similar to "hypothetical") is the difference between ponsegromab and placebo in mean change from baseline in 6MWD at Week 22, in participants with HF and serum GDF-15 concentrations CCI pg/mL, under the scenario of no discontinuation of study intervention and without the potential confounding effect of prohibited procedures or participants' non-compliance with dosing.

 To compare the effect of ponsegromab versus placebo on fatigue reported by participants with HF and serum GDF-15 concentrations CCI pg/mL. 	
 Change from baseline in PROMIS Fatigue 7a at Week 22. 	
 Estimand 5 (similar to "hypothetical") is the difference between ponsegromab and placebo in mean change from baseline in PROMIS Fatigue 7a at Week 22 in participants with HF and serum GDF-15 concentrations CCI pg/mL, under the scenario of no discontinuation of study intervention and without the potential confounding effect of prohibited procedures or participants' non-compliance with dosing.

 To describe the safety and tolerability of ponsegromab in participants with HF. 	
 Incidence of TEAEs, TSEAEs, abnormal laboratory results, and vital signs. 	
 There are no defined estimands for the incidence of TEAEs, TSEAEs, abnormal laboratory results, and vital signs, and these endpoints will be analyzed using Pfizer data standards as applicable.

Objectives	Endpoints	Estimands
Tertiary/Exploratory:	Tertiary/Exploratory:	Tertiary/Exploratory:

 To compare the effect of ponsegromab 300 mg versus placebo, on HF disease-specific health status in participants with HF and any serum GDF-15 concentration. 	
 Change from baseline in KCCQ-23 CSS, OSS, TSS, and physical limitation at Week 22. Responses as defined by a ≥ 5-point increase from baseline in KCCQ-23 CSS, OSS, TSS, and physical limitation at Week 22. 	
 Not applicable.

 To compare the effect of ponsegromab 300 mg versus placebo on the physical function of participants with HF and any serum GDF-15 concentration. 	
 Change from baseline in 6MWD at Week 22. 	
 Not applicable.

 To compare the effect of ponsegromab 300 mg versus placebo on fatigue reported by participants with HF and any serum GDF-15 concentration. 	
 Change from baseline in PROMIS Fatigue 7a at Week 22. 	
 Not applicable.

 To compare the effect of ponsegromab versus placebo on HF disease-specific health status in participants with HF. 	
 Response as defined by a ≥ 10-point and ≥ 15-point increase in KCCQ-23 CSS, OSS, TSS, and physical limitation at Week 22. 	
 Not applicable.

 To describe the effect of ponsegromab on impressions of disease severity and change in participants with HF. 	
 Absolute and change from baseline in PGI-S at Week 22. Absolute PGI-C at Week 22. 	
 Not applicable.

 To compare the effect of ponsegromab versus placebo on body weight in participants with HF. 	
 Change from baseline in body weight at Week 22. 	
 Not applicable.

 To compare the effect of ponsegromab versus placebo on daily activity measures based on accelerometry in participants with HF. 	
 Change from baseline in daily activity measures based on accelerometry at Week 22. 	
 Not applicable.

 To evaluate the PK of ponsegromab in participants with HF. 	
 Serum unbound and total ponsegromab concentrations on Day 1 (predose) and Weeks 4, 8, 12, 16, 20, 22, 24, and 32. 	
 Not applicable.

 To compare the effect of ponsegromab versus placebo on GDF-15 concentrations in participants with HF. 	
 Serum concentrations of GDF-15 on Day 1 and Weeks 4, 8, 12, 16, 20, 22, 24, and 32. 	
 Not applicable.

 To characterize the immunogenicity of ponsegromab in participants with HF. 	
 Incidence of anti-ponsegromab antibodies, and neutralizing antibodies. 	
 Not applicable.

 To compare the effect of ponsegromab versus placebo on markers to check HF risk, acute MI, 	
 Fold change from baseline in NT-proBNP, hsCRP, albumin and pre-albumin at Week 22. 	
 Not applicable.

Objectives	Endpoints	Estimands
inflammation, and nutritional status in participants with HF.		

 To compare the effect of ponsegromab versus placebo on CCI in participants with HF. 	
 Fold change from baseline in CCI at Weeks 12 and 22. Fold change from baseline in CCI at Weeks 12 and 22 (Cohorts C and D only). 	
 Not applicable.

 To compare the effect of ponsegromab versus placebo on clinical outcomes of cardiovascular death, hospitalization for HF, or urgent HF visit and on days alive and out of the hospital in participants with HF. 	
 Hierarchical composite endpoint: 
 Time to cardiovascular death; Number of worsening HF events (hospitalization for HF, or urgent HF visit); Time to first worsening HF event (hospitalization for HF, or urgent heart visit); Change from baseline in KCCQ-23 CSS at Week 22. Time to first occurrence of the clinical composite of cardiovascular death, hospitalization for HF, or urgent heart visit. Total number of days alive and out of the hospital over 22 weeks. Total number of hospitalizations for HF and urgent HF visits over 22 weeks. 	
 Not applicable.

3.2. Open-Label, PK Cohort (Cohort B)

Objectives	Endpoints	Estimands
Secondary:	Secondary:	Secondary:

 To evaluate the safety and tolerability of ponsegromab in participants with HF and elevated circulating GDF-15 concentrations. 	
 Incidence of TEAEs, TSEAEs, abnormal laboratory results, and vital signs. 	
 There are no defined estimands for the incidence of TEAEs, TSEAEs, abnormal laboratory results, and vital signs, and these endpoints will be analyzed using Pfizer data standards as applicable.
Tertiary/Exploratory:	Tertiary/Exploratory:	Tertiary/Exploratory:

 To evaluate the PK of ponsegromab following repeated SC administration in participants with HF and elevated circulating GDF-15 concentrations. 	
 Serum unbound and total ponsegromab PK parameters after 1st dose on Day 1 and 4th dose on Day 85: AUC_{tau}, C_{max}, T_{max} and as data permit, t_{1/2}, CL/F, Vz/F, PTR after 4th dose. 	
 There are no defined estimands for PK endpoints.

 To characterize the effect of ponsegromab on circulating GDF-15 concentrations in participants 	Serum concentrations of GDF-15 on Day 1 and Weeks 1, 2, 3, 4, 8, 12, 13, 14, 15, 16 and 18.	
 Not applicable

Objectives	Endpoints	Estimands
with HF and elevated circulating GDF-15 concentrations.		

 To characterize the immunogenicity of ponsegromab in participants with HF and elevated circulating GDF-15 concentrations. 	
 Incidence of ADA, and NAb. 	
 Not applicable.

 To evaluate the effect of ponsegromab on NT-proBNP in participants with HF and elevated circulating GDF-15 concentrations. 	
 Fold change from baseline in NT-proBNP at Weeks 12 and 16. 	
 Not applicable.

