CCI (Cohorts C and D only)			X			X			X					Sample collected on Day 1 should be collected prior to dosing. Otherwise, timing of sample collection is random. Refer to Section 8.7.2 .
Exploratory Plasma Biomarker			X						X					Refer to Section 8.7.2 . Day 1 sample collected prior to dosing. Also, refer to Section 8.7.8 .
Retained research samples														
Pfizer Retained Research Samples (Prep D1 K2EDTA whole blood, Prep B1 plasma, Prep B2 serum, Prep R1 PAXgene whole blood)			X						X					See Section 8.6.2 Prep D1 collected at Day 1 visit only, predose. If not collected on Day 1, collect at the next available time point when biospecimens are being collected. Also, refer to Section 8.7.6 .
TIMI retained research samples (K2EDTA whole blood, plasma, serum)			X						X					Section 8.6.3 K2EDTA whole blood sample should be collected at Day 1 visit only, predose. Also, refer to Section 8.7.7 .

Table 2. Study Schedule of Activities for Open-Label, PK Cohort (Cohort B) Only

Visit Identifier See abbreviations in Appendix 11 .	SV	Week 0	Week 1	Week 2	Week 3	Week 4	Week 8	Week 12 EoT	Week 13	Week 14	Week 15	Week 16 F/U1	Week 18	Week 22 F/U2	Early Term	Notes
Study day	No earlier than -56	1	8	15	22	29	57	85	92	99	106	113	127	155		Study day relative to start of study intervention (Day 1).
Visit Window (days)	N/A	N/A	±2	±2	±2	±2	±3	±2	±1	±2	±2	±3	±3	±3	N/A	
Visit Location	On-site	On-site or at home				On-site			On-site or at home			On-site	On-site or at home	On-site	ne” refers to participant’s home or current residence	
Informed consent	X															See Section 10.1.3 .
Screen for eligibility	X															See Section 5.1 and Section 5.2 . Screening will be conducted at SV. See Section 8.1.1 .
Demographics	X															
Randomization		X														Randomization occurs following confirmation of eligibility. See Section 6.3 .
Medical history	X															
Physical examination	X	X										X				See Section 8.3.1 . Brief physical examinations to be completed before administration of study intervention.
Height and Weight	X	X				X	X	X				X				See Section 8.3.1 . Height will only be collected at SV.
Vital Signs	X	X				X	X	X				X				See Section 8.3.2 .
12-Lead ECG		X										X				See Section 8.3.3 .
Contraception check	X	X				X	X	X				X		X	X	Refer Appendix 4 . Contraception through Week 20 will be confirmed at the Week 22 visit.
AE/SAE monitoring	X	→	→	→	→	→	→	→	→	→	→	→	→	X	X	See Section 8.4 and Section 8.4.3 .

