Study Intervention and Other Treatments																See Section 6 .
Open-Label placebo injection	X															At SV only, open-label SC placebo will be administered to assess tolerability (see Section 8.1.1).

Table 2. Study Schedule of Activities for Open-Label, PK Cohort (Cohort B) Only

Visit Identifier See abbreviations in Appendix 11 .	SV	Week 0	Week 1	Week 2	Week 3	Week 4	Week 8	Week 12 EoT	Week 13	Week 14	Week 15	Week 16 F/U1	Week 18	Week 22 F/U2	Early Term	Notes
Study day	No earlier than -56	1	8	15	22	29	57	85	92	99	106	113	127	155		Study day relative to start of study intervention (Day 1).
Visit Window (days)	N/A	N/A	±2	±2	±2	±2	±3	±2	±1	±2	±2	±3	±3	±3	N/A	
Visit Location	On-site	On-site or at home				On-site			On-site or at home			On-site	On-site or at home		On-site	ne” refers to participant’s home or current residence
Open-Label, Study intervention administration		X				X	X	X								See Section 6.1 .
Prior/concomitant treatment(s)	X	→	→	→	→	→	→	→	→	→	→	→	→	X	X	See Section 6.9 .
Laboratory Assessments																Refer to lab manual for collection volumes.
Hematology and blood chemistry	X	X						X				X			X	See Appendix 2 . Samples on dosing days must be collected prior to dosing.
Lipid panel		X						X							X	
Pregnancy test	X	X				X	X	X				X		X	X	Refer to Section 8.3.5 . Serum pregnancy only at SV. Urine or serum pregnancy tests collected and analyzed locally at all other timepoints.
Ponsegromab PK		X	X	X	X	X	X	X	X	X	X	X	X		X	Refer to Section 8.5 . PK samples collected on dosing days must be collected prior to dosing.
Immunogenicity (ADA/NAb)		X				X	X	X				X	X		X	Refer to Section 8.7.8 . Samples collected on dosing visits must be collected prior to dosing.
Biomarker Assessments																See laboratory manual.
GDF-15 CCI	X															Required for eligibility. Refer to Section 8.7.1 .
CCI																

Table 2. Study Schedule of Activities for Open-Label, PK Cohort (Cohort B) Only

Visit Identifier See abbreviations in Appendix 11 .	SV	Week 0	Week 1	Week 2	Week 3	Week 4	Week 8	Week 12 EoT	Week 13	Week 14	Week 15	Week 16 F/U1	Week 18	Week 22 F/U2	Early Term	Notes
Study day	No earlier than -56	1	8	15	22	29	57	85	92	99	106	113	127	155		Study day relative to start of study intervention (Day 1).
Visit Window (days)	N/A	N/A	±2	±2	±2	±2	±3	±2	±1	±2	±2	±3	±3	±3	N/A	
Visit Location	On-site	On-site or at home				On-site			On-site or at home			On- site	On-site or at home	On- site	ne” refers to participant’s home or current residence	

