2.2.2.2. Summary of Pharmacokinetics

Following single dose administration of ponsegromab to healthy non-Japanese participants, SC absorption of unbound ponsegromab for the 3 to 300 mg dose groups occurred with median T_{max} ranging from 2.25 to 7.00 days. In general, over the 10 to 300 mg dose range, increases in geometric mean unbound C_{max} in serum were approximately dose-proportional and increases in unbound AUC_{last} and AUC_{inf} in serum appeared to be greater than dose-proportional. The geometric mean CL/F appeared to decrease with increasing dose, and mean terminal $t_{1/2}$ increased with increasing dose, ranging from 3.52 to 11.1 days across the 10 to 300 mg dose groups.

Following single doses of SC ponsegromab in healthy participants, absorption of total ponsegromab occurred with median T_{max} ranging from 6.00 to 14.0 days across the 1 to 300 mg dose groups. In general, increases in geometric mean total C_{max} , AUC_{last} , and AUC_{inf} in serum appeared to be less than dose-proportional over the 10 to 100 mg dose range, while increases in exposure from 100 to 300 mg doses were largely dose proportional. The mean terminal $t_{1/2}$ values increased from 20.1 days for the 10 mg group to 30.9 days for the 300 mg group. The long terminal $t_{1/2}$ of total ponsegromab in serum is driven primarily by the half-life of bound ponsegromab (ponsegromab-GDF-15 complex), as the terminal $t_{1/2}$ of unbound ponsegromab observed over the same dose range was much shorter. Unbound ponsegromab (not total ponsegromab) is the active moiety that accounts for pharmacological activity of the drug.

CCI [REDACTED]

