**Table 2. Derivation of Ponsegromab PK Parameters**

Parameter	Day(s)	Definition	Method of Determination
AUC tau	1, 85	Area under the plasma concentration-time profile from time zero to time tau, the dosing interval, where tau = 28 days for Q4W dosing.	Linear/Log trapezoidal method
C max	1, 85	Maximum plasma concentration during the dosing interval	Observed directly from data
T max	1, 85	Time for C max	Observed directly from data as time of first occurrence
AUC tau (dn)	1, 85	Dose normalized AUC tau	AUC tau /Dose
C max (dn)	1, 85	Dose normalized C max	C max /Dose
C min	1, 85	Minimum plasma concentration during the dosing interval	Observed directly from data
CL/F	85	Apparent clearance for oral dosing	Dose/AUC tau
R ac	85	Observed accumulation ratio	Day 85 AUC tau /Day 1 AUC tau
R ac , C max	85	Observed accumulation ratio for C max	Day 85 C max /Day 1 C max
PTR	85	Peak-to-trough ratio	C max /C min
t 1/2 *	85	Terminal half-life	Loge(2)/kel, where kel is the terminal phase elimination rate constant calculated by a linear regression of the log-linear concentration-time curve
V z /F*	85	Apparent volume of distribution for oral dosing	Dose/(AUC tau * kel)

\*As data permits.

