NAb-negative subject	NAb evaluable participant who is either (1) an ADA-negative subject or (2) an ADA-positive subject without treatment-induced or treatment-boosted NAb response (i.e. subject has all NAb-negative results throughout the study or subject is NAb positive at baseline but did not become treatment-boosted post-dose). Note: in the event a subject is ADA-positive at baseline but did not show a boosted response post-treatment, subject is classified as ADA-negative and NAb-negative at the subject level even if the subject has post-treatment positive NAb titer. As such all ADA-negative subjects are NAb-negative regardless of NAb titer data."
NAb incidence	The percent of NAb-positive subjects in a treatment group/cohort or study.
Duration of ADA and NAb response (subject-level definitions): recommended for studies with <math>\geq 16</math> weeks of ADA measurements	
Transient ADA	An ADA-positive subject with (1) a treatment-induced or treatment-boosted ADA sample detected only at 1 sampling time (excluding the last time point) post-treatment, or (2) treatment-induced or treatment-boosted ADA samples detected at $\geq 2$ time points where the first and last positive samples (irrespective of any negative samples in between) are separated by $< 16$ weeks, and the subject's last sample is ADA negative.
Persistent ADA	An ADA-positive subject with first and last positive ADA samples (treatment-induced or treatment-boosted) detected over a period of $\geq 16$ weeks post-treatment, irrespective of any negative samples in between.
Indeterminate ADA	An ADA-positive subject who is not persistent or transient.
Transient NAb	A NAb-positive subject with (1) a treatment-induced or treatment-boosted NAb sample detected only at 1 sampling time (excluding the last time point) post-treatment, or (2) treatment-induced or treatment-boosted NAb samples detected at $\geq 2$ time points where the first and last positive samples (irrespective of any negative samples in between) are separated by $< 16$ weeks, and the subject's last sample is NAb negative or ADA negative.
Persistent NAb	A NAb-positive subject with first and last positive NAb samples (treatment-induced or treatment-boosted) detected over a period of $\geq 16$ weeks post-treatment, irrespective of any negative samples in between.
Indeterminate NAb	A NAb-positive subject who is not persistent or transient.

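### Cohort B schedules no PK or ADA/NAb sample at its Week 22 visit, so total-drug half-life and Vz/F will be imprecise and persistent ADA cannot be reached on scheduled samples

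*Protocol*

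**What the plan says.** Protocol Table 2 (Section 1.3) gives the Cohort B study days as "No earlier than -56 1 8 15 22 29 57 85 92 99 106 113 127 155", so dose 4 falls on Day 85 (Week 12), Week 18 is Day 127, and Week 22 (F/U2, on site) is Day 155.

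The PK row reads "Ponsegromab PK X X X X X X X X X X X X X". The 13 marks are Weeks 0, 1, 2, 3, 4, 8, 12, 13, 14, 15, 16 and 18, plus Early Termination. The ADA row reads "Immunogenicity (ADA/NAb) X X X X X X X". Its seven marks are Weeks 0, 4, 8, 12, 16 and 18, plus Early Termination. The Week 22 cell is blank in both rows.

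The post-screening GDF-15 row of Table 2 is redacted, so the source for GDF-15 is the endpoint list in Protocol 3.2: "Serum concentrations of GDF-15 on Day 1 and Weeks 1, 2, 3, 4, 8, 12, 13, 14, 15, 16 and 18".

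Protocol 3.2 lists half-life and Vz/F of total and unbound drug after dose 4 as exploratory endpoints, conditional on the data allowing them. SAP Table 2 derives half-life from kel, the "terminal phase elimination rate constant calculated by a linear regression of the log-linear concentration-time curve", and Vz/F as Dose/(AUCtau × kel).

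For immunogenicity, SAP 6.3.17 sends Cohort B to Section 6.3.11, which allows a listing of ADA and NAb duration where appropriate. Appendix 6 defines persistent ADA as "An ADA-positive subject with first and last positive ADA samples" at least 16 weeks apart after treatment. The NAb class follows the same rule.

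**The concern.** Cohort B exists mainly to characterise PK and the PK/PD relationship, and it is the only cohort with a PK parameter analysis set. Total drug clears slowly: Protocol 2.2.2.2 reports a terminal half-life rising from 20.1 days at 10 mg "to 30.9 days for the 300 mg group". A slope fitted over roughly one half-life is weakly determined, and half-life and Vz/F both inherit its error.

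The ADA duration classes raise a separate matter of arithmetic. If scheduled sampling is shorter than the defining interval, a participant who is positive at every post-dose visit would be tabulated as *indeterminate*. A reader could take that as a finding about the drug when it comes from the schedule.

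Both limits arise although the visit that would relieve them already takes place.

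**Working it through.** The plan states no precision figure for these parameters, so there is none to reproduce. The checks use the schedule and the stated half-lives.

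**1. Points available after dose 4.** For PK, "PK samples collected on dosing days must be collected prior to dosing", so the Week 12 sample precedes dose 4. The later samples are Weeks 13, 14, 15, 16 and 18, that is days 7, 14, 21, 28 and 42 after the dose. Week 22 is day 155 − 85 = 70.

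**2. Half-lives covered, total drug.** Median Tmax is 6 to 14 days (Protocol 2.2.2.2). Post-peak span divided by half-life:

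| Half-life | To Week 18 | To Week 22 |
|---|---|---|
| 30.9 d (300 mg) | 28/30.9 = 0.91 to 36/30.9 = 1.17 | 56/30.9 = 1.81 to 64/30.9 = 2.07 |
| 20.1 d (10 mg, lower bound) | 28/20.1 = 1.39 to 36/20.1 = 1.79 | 56/20.1 = 2.79 to 64/20.1 = 3.18 |

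The protocol gives no value for 100 or 200 mg.

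**3. Precision of kel in one participant.** For a log-linear regression, CV(kel) = σ/(√Sxx × kel), with kel = ln 2/half-life: 0.0224 per day at 30.9 d and 0.0345 per day at 20.1 d. The residual σ is an assumption, taken as 0.15 on the log scale. Day 7 is used only if the peak has passed by then.

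| Days after dose 4 | Sxx | CV(kel), 30.9 d | CV(kel), 20.1 d |
|---|---|---|---|
| 14, 21, 28, 42 | 428.75 | 32% | 21% |
| same + 70 | 1960 | 15% | 10% |
| 7, 14, 21, 28, 42 | 725.2 | 25% | 16% |
| same + 70 | 2613.3 | 13% | 9% |

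First row, 30.9 d: 0.15/(20.71 × 0.0224) = 0.32. The CV is proportional to σ: for the four-point set at 30.9 d, σ of 0.10 to 0.20 gives 22% to 43%, and 10% to 20% once day 70 is added.

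**4. ADA span.** Week 4 to Week 18 is 127 − 29 = 98 days = 14.0 weeks. With windows at their limits (Week 4 two days early, Week 18 three days late) it is 130 − 27 = 103 days = 14.7 weeks. The definition needs 112 days. With a Week 22 sample the span is 155 − 29 = 126 days = 18.0 weeks, and 152 − 31 = 121 days at the least favourable windows. This helps only a participant first positive at Week 4, because Week 8 to Week 22 is 98 days, or 104 at most.

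**5. Unbound drug.** At its longest stated half-life, 11.1 days, days 14 to 42 cover 28/11.1 = 2.5 half-lives, and dose to day 42 covers 42/11.1 = 3.8.

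**The case against.** The plan already treats half-life and Vz/F as conditional: both are exploratory, and SAP 5.3.3 codes a parameter that cannot be derived as not calculated and leaves it out of summaries. AUCtau, Cmax and CL/F do not need Week 22. Unbound drug, which the protocol names as the active moiety, is adequately followed. Cohorts A, C and D sample PK and ADA to Week 32, 84 days after the last dose. The 30.9-day figure is for 300 mg, planned for 8 of about 20 participants. All of this stands and limits the weight of the point. It does not supply the noncompartmental total-drug parameters, which are planned for Cohort B alone.

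A reader might infer that persistent ADA can never occur in Cohort B. The documents do not support that. Protocol 8.8 permits further samples about every 90 days from participants still ADA-positive at study end, Section 7.1 permits sampling for unresolved adverse events possibly related to ADA, and an Early Termination sample from about Day 141 (29 + 112) would also reach 16 weeks. These routes are discretionary or incidental, and with no ADA sample scheduled at study end the trigger in 8.8 would normally rest on the Week 18 result.

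A reader might also infer that total-drug half-life and Vz/F will be unreportable. That needs an acceptance threshold, and the documents give none. SAP 5.3.3 defers to sponsor rules that are not included.

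Nor was Cohort B set up to measure ADA duration or the return of GDF-15. Its listed immunogenicity endpoint is incidence. Treatment-induced ADA was 0 and 9.1% (1 of 11) in the two cancer studies, so about 0 to 2 of 20 participants might be classified at all.

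**Conclusion.** The point holds as a limited, inexpensive improvement to exploratory results. Scheduled PK and ADA/NAb sampling, and the GDF-15 endpoint list, end 42 days after dose 4 although participants return on day 70.

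- **Total-drug half-life and Vz/F** will be imprecise. At 30.9 days the per-participant CV of kel is about 25 to 32%, and a Week 22 sample roughly halves it to 13 to 15%. This rests on an assumed 15% residual CV and on half-lives from healthy participants after a single dose. If the half-life is nearer 20.1 days, the problem is smaller.
- **Persistent ADA or NAb** cannot be reached on scheduled samples: 14.0 weeks, at most 14.7, against 16. This needs no assumption beyond the visit schedule.

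Unbound drug, AUCtau, Cmax, CL/F and ADA incidence are not affected.

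**What to change.** In Protocol Table 2, add PK, GDF-15 and ADA/NAb samples at the existing Week 22 (F/U2) visit, and add Week 22 to the Cohort B GDF-15 endpoint in Section 3.2. The cost is 4 mL (PK) + 6 mL (GDF-15) + 4 mL (ADA/NAb) = 14 mL on a stated total of about 184 mL, plus the assays, in about 20 participants. No visit is added.

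If the schedule cannot change, amend the SAP only. Section 6.3.17 should say that ADA and NAb duration classes are not reported for Cohort B, and SAP Table 2 or Section 6.3.15 should flag total-drug half-life and Vz/F as limited by the sampling span. That costs two sentences.
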